10.2.7. Amputation and Mortality Rate

The rates of amputation, limb salvage and mortality will be analyzed for all treated subjects per actual treatment using the method for time-to-event variables. The probability of being event-free at 6 and 12 months will be summarized for each treatment arm and compared vs. Placebo using a Log Rank test.

The duration of time to amputation will be defined as the number of days between the day of amputation – the first dose date + 1. If a subject does not report amputation, then the date that the subject will be censored at the date of study discontinuation. If the date of study discontinuation is not available, then the subject's censor date will be the last known visit the subject attended. The same calculation will be repeated for limb salvage and mortality (time to death).

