6.2.2. SECONDARY EFFICACY ENDPOINTS

Other secondary endpoints will include:

- Difference in pain level between baseline and the 9 month follow-up as determined by VAS by sex and by comorbidities (esp. diabetes or renal dysfunction)
- Change in tissue oxygenation (TcPO₂) from baseline to 6, 9 and 12 months following the first treatment
- Change in hemodynamic measures (ABI and TBI) from baseline to Day 28, Day 90, 6 months, 9 months and 12 months following the first treatment
- Change in perfusion (MRA) from baseline to 9 months following the first treatment
- Wound healing (no ulcer: change of skin condition, one ulcer: change of ulcer size, multiple ulcer: change of ulcer number) from baseline to 9 months following the first treatment
- Change in VAS score from baseline to Day 14, Day 28, Day 42, Day 90, at 6 months, 9 months, and 12 months.
- Change in QOL score (VascuQol) at 90 Days, 9 months and 12 months;
- Major limb amputation rate at six months and twelve months following the first treatment
- Mortality at six and twelve months after first treatment

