3. STUDY OVERVIEW

This is a 12 month Phase II, double-blind, randomized, placebo-controlled, multi-center study designed to assess the safety and efficacy of VM202 in subjects with critical limb ischemia.

Subjects who meet the eligibility criteria will be randomized in a 2:2:1 ratio to one of three treatment arms: Low Dose (8 mg VM202), High Dose (16 mg VM202) or placebo, respectively.

Subjects in the Low Dose Group (8 mg VM202) will receive:

- Day 0: 4 mg of VM202 (16 injections of 0.5 ml of VM202)
- Day 14: 4 mg of VM202 (16 injections of 0.5 ml of VM202)
- Day 28: Placebo only (16 injection of 0.5 ml normal saline)
- Day 42: Placebo only (16 injection of 0.5 ml normal saline)

Subjects in the High Dose Group (16 mg VM202) will receive:

- Day 0: 4 mg of VM202 (16 injections of 0.5 ml of VM202)
- Day 14: 4 mg of VM202 (16 injections of 0.5 ml of VM202)
- Day 28: 4 mg of VM202 (16 injections of 0.5 ml of VM202)
- Day 42: 4 mg of VM202 (16 injections of 0.5 ml of VM202)

Subjects in the placebo control group will receive 16 injections of 0.5 ml normal saline at each visit.

Table 1 lists the final dose and dose per visit to be administered by study arm.

Table 1. VM202 administration for each study arm

TREATMENT GROUP	FINAL DOSE VM202	DOSE VM202 (MG) PER VISIT			
		DAY 0	DAY 14	DAY 28	DAY 42
Low Dose	8 mg	4	4	0	0
High Dose	16 mg	4	4	4	4
Placebo	0	0	0	0	0

The schedule of study visits and the clinical parameters that will be measured at the visits are summarized in Table 2 below.

TABLE 2 SCHEDULE OF EVALUATIONS AND VISITS

PROCEDURE	Screening / Baseline (-30 – 0 D)	1 st Injection Day 0		2 nd Injection Day 14 ± 3 D		3 rd Injection Day 28 ± 3 D		4 th Injection Day 42 ± 3 D		Day 49 ± 3 D	Day 90 ± 7 D	6 mo ± 1 mo	9 mo ± 1 mo	12 mo ± 1 mo	Early Withdrawal
		Pre-dose	Post-dose	Pre-dose	Post-dose	Pre-dose	Post-dose	Pre-dose	Post-dose						
Baseline Evaluation															
Informed Consent	✓														
Complete Medical History	✓														
Complete Physical Exam	✓														
Cancer screening [†]	✓														
Viral screening – HIV, HTLV, HBV, HCV	✓														
Urinalysis	✓														
ECG	✓														
Pregnancy test	✓														
Safety and Efficacy Parameters															
Retinal Fundoscopy	✓													✓	✓
Vital Signs	✓	✓	✓	✓	✓	✓	✓	✓	✓	✓	✓	✓	✓	✓	✓
Concomitant Medications	✓	✓		✓	✓		✓	✓		✓	✓	✓	✓	✓	✓
Serum Chemistry and hematology	✓	✓		✓	✓		✓	✓		✓	✓	✓	✓	✓	✓
Photograph and measurement of ulcer(s) ^{††}	✓	✓		✓	✓		✓	✓		✓	✓	✓	✓	✓	✓

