5.2. Statistical Methods

Two-sided p -values < 0.05 will be considered statistically significant, unless otherwise stated.

Separate statistical tests will be performed at each time point for key endpoints of interest.

In general, an overall test to determine if there is a statistically significant difference among the three treatment arms will be conducted first. Further comparisons will be made to determine if either the low or high dose groups are significantly different from the placebo group.

For continuous variables, a one-way analysis of variance (ANOVA) with treatment group (high dose, low dose, and placebo) as a factor will be used to determine if there is a significant difference among the groups. The low and high dose groups will each be compared against the placebo group using Dunnett's test. The mean difference between the VM202 groups versus placebo along with 95% confidence intervals for the mean difference will also be presented. To be viewed as secondary, an additional set of analyses will be run using non-parametric tests. A Jonckheere-Tepstra test will be applied to the VAS change from baseline results to detect overall trend differences. Non-parametric pairwise treatment comparisons versus placebo will also be made using Wilcoxon Rank Sum test. Within each treatment group for each endpoint, both a paired t-test (parametric) and Wilcoxon Signed Rank test will be run to test for differences comparing baseline to each post-baseline assessment.

For categorical variables, Fisher's exact test will be used to determine if there is a significant difference among the three treatment groups. Separate Fisher's exact tests will be used to compare the low and high dose groups to the placebo group.

For time-to-event variables (such as amputation, limb salvage and mortality), Kaplan-Meier estimates will be used to estimate survival times. Differences in survival times will be compared among groups using the log-rank test.

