Programmer Note Tables 10.2, 10.3, 10.4, 10.5 and 10.6 will be identical to Table 10.1 for the other domain scores (Symptom, Pain, Emotional, and Social), Total score and Resting Pain Please make change to the footnote for the score definition accordingly.

Programmer Note Table 10.7 will be identical to Table 10.1 for each individual question.

Table 11.1.1
Amputation– Event Free Probability
Per-Protocol Population

Amputation	Placebo (N=)	VM202- 8 mg (N=)	VM202- 16 mg (N=)
Number (%) of Subjects Who Had Amputation	n (%)	n (%)	n (%)
Number (%) of Subjects Censored	n (%)	n (%)	n (%)
Quartiles [95% CI] (days)			
25 th Percentile	xx (xx.x, xx.x)	xx (xx.x, xx.x)	xx (xx.x, xx.x)
50 th Percentile	xx (xx.x, xx.x)	xx (xx.x, xx.x)	xx (xx.x, xx.x)
75 th Percentile	xx (xx.x, xx.x)	xx (xx.x, xx.x)	xx (xx.x, xx.x)
p-value ^[1]		xxxx	xxxx
Kaplan Meier Estimate (# at Risk)			
6 Months	x.xxxx (n)	x.xxxx (n)	x.xxxx (n)
12 Months	x.xxxx (n)	x.xxxx (n)	x.xxxx (n)
Range (days)			
Subjects with an Event	xx, xx	xx, xx	xx, xx
All Subjects	xx, xx	xx, xx	xx, xx

^[1] P-value tests for treatment difference using log rank test.
path\t_program.sas date time

Programmer Note Tables 11.1.2 will be identical to Table 11.1.1 for the ITT Population.
Programmer Note For censoring rules, see Section 10.2.7 of the Statistical Analysis Plan.

Table 11.2.1
Limb Salvage – Event Free Probability
Per-Protocol Population

Limb Salvage	Placebo (N=)	VM202- 8 mg (N=)	VM202- 16 mg (N=)
Number (%) of Subjects Who Had a Limb Salvage Procedure Performed	n (%)	n (%)	n (%)
Number (%) of Subjects Censored	n (%)	n (%)	n (%)
Quartiles [95% CI] (days)			
25 th Percentile	xx (xx.x, xx.x)	xx (xx.x, xx.x)	xx (xx.x, xx.x)
50 th Percentile	xx (xx.x, xx.x)	xx (xx.x, xx.x)	xx (xx.x, xx.x)
75 th Percentile	xx (xx.x, xx.x)	xx (xx.x, xx.x)	xx (xx.x, xx.x)
p-value ^[1]		x.XXXX	x.XXXX
Kaplan Meier Estimate (# at Risk)			
6 Months	x.XXXX (n)	x.XXXX (n)	x.XXXX (n)
12 Months	x.XXXX (n)	x.XXXX (n)	x.XXXX (n)
Range (days)			
Subjects with an Event	xx, xx	xx, xx	xx, xx
All Subjects	xx, xx	xx, xx	xx, xx

^[1] P-value test for treatment difference using log rank test.

path\t_program.sas date time

Programmer Note Tables 11.1.2 will be identical to Table 11.1.1 for the ITT Population.

Programmer Note For censoring rules, see Section 10.2.7 of the Statistical Analysis Plan.

Table 11.3.1
Mortality – Event Free Probability
Per-Protocol Population

Mortality	Placebo (N=)	VM202- 8 mg (N=)	VM202- 16 mg (N=)

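### SAP 10.2.7 compares 6- and 12-month event-free probabilities by a whole-curve log-rank test, and the table shells give those fixed-time endpoints no confidence interval and no difference from placebo

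*SAP*

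**What the plan says.** Protocol 6.2.2 lists two fixed-time secondary endpoints: "Major limb amputation rate at six months and twelve months following the first treatment" and "Mortality at six and twelve months after first treatment".

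SAP 10.2.7 sends amputation, limb salvage and mortality to the time-to-event method, and then says: "The probability of being event-free at 6 and 12 months will be summarized for each treatment arm and compared vs. Placebo". The full phrase on the test is "compared vs. Placebo using a Log Rank test". SAP 5.2 describes that method as Kaplan-Meier estimation with a test of the whole event-time distribution: "Differences in survival times will be compared among groups using the log-rank test".

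The censoring rule does not cut follow-up at 6 months. For a patient without the event, "the subject will be censored at the date of study discontinuation", or at the last visit attended if that date is missing. The study lasts 12 months (SAP 3), and the last visit has a window of one month either side.

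In SAP Appendix B, shells 11.1.1, 11.2.1 and 11.3.1 have one p-value per dose, footnoted in 11.1.1 as "P-value tests for treatment difference using log rank test" (the other two are worded almost identically). It stands below the quartiles of event time, which carry 95% CIs. The 6- and 12-month Kaplan-Meier rows come after it and show the estimate and the number at risk only. Neither document gives a fixed-time test, an interval, or a difference from placebo for these probabilities.

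**The concern.** The 10.2.7 sentence names one quantity and assigns a test of another. The protocol asks two questions per event (6 months, 12 months). The plan returns one answer per event and dose, which pools information from every event time. Under proportional hazards the null hypotheses coincide, but the SAP does not state that assumption. A constant hazard ratio from Day 0 is also not obvious here: dosing runs to Day 42, the proposed mechanism is new vessel growth (Protocol 1.8), and patients who will need amputation within 4 weeks are excluded.

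Two things are at stake. A reader who follows 10.2.7 could take the log-rank p-value as the verdict on the 6-month rate when it says little about it. And limb-loss and mortality rates from 10 placebo patients would be printed without any statement of precision, although SAP 4 gives estimation for a pivotal study as the reason for the sample size.

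**Working it through.** **Inputs.** Arms of 20, 20 and 10 (SAP 4). Two-sided 0.05 (SAP 5.2). Follow-up of 12 months. One-year amputation-free survival of 45% (Protocol 1.3.3), used only as an anchor; a constant hazard (assumption) then gives √0.45 = 0.67 at 6 months. All other event rates are assumptions. The documents give no power or event count for these endpoints, so there is no figure of theirs to reproduce.

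**Formulas.** Log-rank: χ² = (O − E)²/V, with O, E and V summed over all event times. Fixed-time test at time t: z = (θ₀ − θ₁)/√(v₀ + v₁), with θ = ln(−ln S) and, when nobody is censored before t, v = [(1 − S)/(nS)]/(ln S)². Difference S₁ − S₀: SE = √[S₀(1 − S₀)/n₀ + S₁(1 − S₁)/n₁].

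**Example 1: different at 6 months, equal at 12.** Placebo (n = 10) has events at months 1, 2, 3, 4, 5. Active (n = 20) has events at 2, 4, 5, 7, 8, 9, 9.5, 10, 10.5, 11. The rest are event-free at month 12.
- Event-free at 6 months: 5/10 = 0.50 vs 17/20 = 0.85. At 12 months: 0.50 vs 10/20 = 0.50.
- Planned log-rank (active arm): O = 10, E = 10.848, V = 2.941, χ² = 0.245, p = 0.62.
- Fixed-time at 6 months: θ = −0.367 and −1.817; v = 0.100/0.480 = 0.208 and 0.00882/0.0264 = 0.334; z = 1.450/√0.542 = 1.97, p = 0.049.
- Difference at 6 months: 0.35, SE = √(0.0250 + 0.0064) = 0.177, 95% CI 0.00 to 0.70. At 12 months: 0, SE = √(0.0250 + 0.0125) = 0.194, 95% CI −0.38 to 0.38.

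**Example 2: equal at 6 months, different at 12.** Placebo events at 2, 4, 7, 8, 9, 10, 11; active events at 1, 2, 4, 5.
- Event-free at 6 months: 0.80 vs 0.80. At 12 months: 0.30 vs 0.80.
- Planned log-rank: O = 4, E = 7.642, V = 2.277, χ² = 5.83, p = 0.016.
- Fixed-time: p = 1.00 at 6 months, p = 0.009 at 12 months.

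One log-rank p-value cannot serve both times in either example.

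**Simulation.** 10 placebo vs 20 active patients, 3,000 trials per row, hazards constant within each half-year, everyone followed to month 12. Entries are the share of trials with p < 0.05.

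| Event-free at 6 mo, placebo / active | At 12 mo | Planned log-rank | Fixed-time, 6 mo |
|---|---|---|---|
| 67% / 67% | 45% / 45% | 5.9% | 3.8% |
| 67% / 67% | 45% / 65% | 16.2% | 3.5% |
| 75% / 75% | 30% / 72% | 47.9% | 3.3% |
| 45% / 85% | 44% / 44% | 15.7% | 61.7% |

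With end of follow-up spread uniformly over Days 335 to 395, repeated runs gave 14% to 16% for the second row. An extreme case (85% event-free in both arms at 6 months; 40% placebo vs 80% active at 12) gave 52% to 56%.

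**How strong are these scenarios?** The placebo-to-active hazard ratio in months 6 to 12 is ln(0.40/0.85)/ln(0.80/0.85) = 12.4 in the extreme case and ln(0.45/0.67)/ln(0.65/0.67) = 13.1 in the milder one. The milder case is mild only in its 12-month gap of 20 percentage points.

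**Would a log-rank censored at 6 months do?** No. With 50% risk in both arms at 6 months, but placebo events mostly by Day 60 and active events mostly after Day 120, it rejected in 15% to 16% of trials. It still compares curves, over a shorter span.

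**Precision.** If 7 of 10 placebo patients were event-free, the exact 95% CI would be 35% to 93%.

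**The case against.** The best case for the plan is that it is mostly right and one sentence is loose. SAP 5.2 describes the log-rank correctly as a comparison of survival times. The shells place its p-value below the event-time quartiles, not beside the 6- and 12-month rows, and the footnotes name the test. Its size is sound: 5.9% in the null row above. These are secondary endpoints in a 50-patient phase II study with no success rule tied to them, and the estimates, numbers at risk and curves are all planned. All of this stands, and it limits the weight of the point.

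It also rules out some stronger readings that a reader might infer. One is that these endpoints have no valid test: the log-rank is a valid test of no treatment effect on the event-time distribution, and what it does not do is isolate a time. Another is that the figure above 50% is a false-positive rate: in that scenario 12-month risk truly differs (60% vs 20%), and 12 months is also a protocol endpoint. A third is that the 12-month endpoint is served as badly as the 6-month one: follow-up ends near month 12, so the mismatch there is smaller, though Example 1 shows that it is not nil.

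What the objection does not answer is that 10.2.7 still says the fixed-time probabilities are compared by this test, and that no output gives their precision or their difference from placebo.

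**Conclusion.** The point holds as a mismatch between endpoint and analysis, with a reporting gap, and not as an invalid test. The planned p-value can be non-significant when the 6-month rates differ widely (15.7% rejection against 61.7% for a fixed-time test) and significant when they are equal (about 15% in the milder scenario, just over 50% in the extreme one). These sizes rest on assumed non-proportional hazards, with a strong contrast between the arms in the second half-year; the documents neither support nor exclude such a pattern. Under proportional hazards the mismatch would matter little. The missing intervals and differences do not depend on any scenario and are the firmer part of the point. The change is worth making because it is cheap and answers the protocol's own endpoints.

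**What to change.** In SAP 10.2.7, separate the two analyses:

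1. For each event, report the Kaplan-Meier event-free probability at 6 and at 12 months with a 95% CI (for example, Greenwood variance on the complementary log-log scale), and the difference of each dose from placebo with a 95% CI at each time.
2. If a p-value at a time point is wanted, use a fixed-time comparison of the Kaplan-Meier estimates, not a log-rank censored at 6 months.
3. Keep the full-follow-up log-rank and label it as a comparison of whole curves.

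State a fallback for an arm with no events, where the Greenwood variance is zero: for example, exact binomial limits for the estimate and Fisher's exact test for a p-value. This could well be needed. If the roughly 25% mortality in Protocol 1.3.3 is read as a one-year figure with a constant hazard (assumption), the chance of no placebo death by 6 months is (√0.75)¹⁰ = 0.75⁵ = 24%.

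In shells 11.1 to 11.3, add the interval to the 6- and 12-month rows, add a difference row for each time, and reword the p-value footnote.

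The cost is one reworded sentence, a few rows in three shells, and no new data. The drawback is that the intervals will be wide: in Example 1 the 6-month difference of 35 percentage points runs from about 0 to 70. That is an accurate account of what 10 placebo patients can show.

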10.1.2. Imputation Methods of VAS Results for the ITT Population

In order to include all subjects in the ITT population, the following imputation rules will be applied for analysis of the ITT population.

For subjects without the primary efficacy endpoint (VAS change from baseline to 9 months), the following imputation methods will be applied:

- For missing Baseline VAS, assign the VAS score at Screening if the VAS score at Day 0 is missing.
- For missing 9 month VAS, assign the 12 month VAS score if the 9 month VAS is missing.

- For missing 9 month VAS, assign the last reported VAS prior to the 9 month VAS visit if both the 9 month and 12 month VAS assessments are missing.

For subjects who had a major amputation or limb procedure carried out, the following imputation methods will be applied:

- For subjects with a major amputation, assign the post baseline VAS score prior to the amputation.
- For subjects with a limb salvage, assign the post baseline VAS score prior to the intervention.

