10.2.3. HEMODYNAMIC ASSESSMENTS (ABI/TBI)

Hemodynamic assessments taken on the index limb and contra-lateral limb include the following:

- Resting Ankle Brachial-Index (ABI) – measurements taken on both legs.
- Resting Toe Brachial-Index (TBI) – measurements taken on toe of right and left foot.

Resting ABI and TBI and the change from baseline (= post-treatment – baseline) will be summarized by index/non-index limb, study visit, and treatment arm using the method for continuous variables. A value of 0 will be assigned if no pulse is reported. Same as the transcutaneous oxygen pressure measurements described in Section 10.2.2, the baseline value is the measurement taken at the Day-0 (Pre-Dose) Visit if the percent difference between the measurements taken at the Screening Visit and the Day-0 Visit is $\leq 15\%$. Otherwise, the baseline value is the average of the measurements taken at Screening and Day-0 Visits. The change in ABI and TBI from baseline will be summarized by study visit and study arm using the method for continuous variables. Supplemental analysis for exploratory purposes may be generated that does not consider subjects who have a baseline TBI/ABI between .9-1.3 mmHg.

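### The protocol's endpoint is major limb amputation, but the SAP analyses amputation at no stated level, and neither document defines major or says which leg counts

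*SAP*

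**What the plan says.** Protocol 6.2.2, and the synopsis in the same words, lists this secondary endpoint: "Major limb amputation rate at six months and twelve months following the first treatment". It does not define *major* and does not name a leg.

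The analysis is in SAP 10.2.7: "The rates of amputation, limb salvage and mortality will be analyzed for all treated subjects per actual treatment". The event time is set as follows: "The duration of time to amputation will be defined as the number of days between the day of amputation" and the first dose date, plus one. The censoring rule begins "If a subject does not report amputation" and sends such a subject to the study discontinuation date, or failing that to the last attended visit. The section gives no anatomical level and no leg.

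The other places that govern this analysis add nothing. SAP 5.2 says "For time-to-event variables (such as amputation, limb salvage and mortality), Kaplan-Meier estimates will be used". The first row of the Table 11.1.1 layout in Appendix B is "Number (%) of Subjects Who Had Amputation". Figure 1 in Appendix C is titled simply as amputation.

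Elsewhere the SAP does make both distinctions. The VAS imputation rule in 10.1.2 reads "For subjects with a major amputation, assign the post baseline VAS score prior to the amputation", and 10.2.1.1, 10.2.2.1, 10.2.3.1, 10.2.6.1 and 10.2.8.1 use the same qualifier. For ABI and TBI, 10.2.3 says that results "will be summarized by index/non-index limb, study visit, and treatment arm".

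**The concern.** The SAP is the document a programmer will follow. On its wording any reported amputation ends a patient's event-free time, whatever its level, so the result would be reported against a protocol endpoint that it does not measure.

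This matters in this population. Eligible patients may have ischemic ulcers or focal gangrene (Protocol 3.3.1, criterion 4), so minor amputations are plausible. SAP 4 gives the purpose of the sample size as estimating effect sizes and variability for a pivotal study. A limb-loss estimate that mixes levels is a poor input to that, whatever its p-value.

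A second gap sits beside the first. Drug is injected in one leg only (Protocol 3.2), but nothing in either document says whether loss of the other leg is an event.

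**Working it through.** The plan states no event count, rate or power for amputation, so there is no figure of its own to reproduce. The check is mainly one of text.

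**1. Event definition, place by place**

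| Place | Level stated | Leg stated |
|---|---|---|
| Protocol synopsis and 6.2.2 (endpoint) | major | no |
| Protocol 3.1 (objective) | lower leg, incidence and extent | no |
| SAP 2.2 (objective) | lower leg, incidence and extent | no |
| SAP 5.2 (method) | none | no |
| SAP 10.2.7 (analysis) | none | no |
| SAP Table 11.1.1 and Figure 1 | none | no |
| SAP 10.1.2 and five other imputation sections | major, undefined | no |

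The level differs between the protocol endpoint and every place in the SAP that analyses it. The leg is absent from all of them, so on the leg the two documents do not disagree.

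**2. What the literal rule does to a patient**

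A Kaplan-Meier analysis gives each patient one event time, by convention the first event. Take a patient with a minor amputation in month 2 and a major one in month 8 (an invented case). The SAP's rule puts the event in month 2, so the patient is a failure at both 6 and 12 months. Under the protocol endpoint the patient is free of major amputation at 6 months and fails only at 12. A patient with a minor amputation alone is a failure under the SAP's rule and never an event under the protocol's. The major-amputation curve cannot be recovered from the resulting table or figure.

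**3. Effect of one patient**

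Planned arm sizes are 20, 20 and 10 (SAP 4). One patient wrongly counted changes the crude rate by:
- placebo: 1/10 = 10 percentage points
- either active arm: 1/20 = 5 percentage points

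These are upper limits at the planned sizes. If the patient has already had a major amputation by the time point, the crude rate there does not change.

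**4. Direction, on assumed rates only**

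The documents give no minor or major amputation rate for this population. Suppose 12-month major amputation is 30% on placebo and 10% on one active arm, and a share q of patients in every arm has a minor or opposite-leg amputation, independently. The any-amputation rate is 1 − (1 − p)(1 − q), and the hazard ratio is ln(1 − active rate) / ln(1 − placebo rate).

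| q | Placebo | Active | Difference | Hazard ratio |
|---|---|---|---|---|
| 0 | 30% | 10% | 20 points | 0.30 |
| 10% | 1 − 0.70 × 0.90 = 37% | 1 − 0.90 × 0.90 = 19% | 18 points | 0.46 |
| 20% | 1 − 0.70 × 0.80 = 44% | 1 − 0.90 × 0.80 = 28% | 16 points | 0.57 |
| 30% | 1 − 0.70 × 0.70 = 51% | 1 − 0.90 × 0.70 = 37% | 14 points | 0.65 |

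With q equal across arms the effect is diluted. If q differed by arm, the distortion could go either way.

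**The case against.** The best reply is that *amputation* in 10.2.7 is shorthand. The imputation bullets themselves write major amputation and then refer back to it as the amputation. The 6- and 12-month time points match the protocol's major-amputation endpoint, and SAP 1 says that the plan serves this protocol. The SAP never says *any* amputation and never mentions toes. What a subject reports also depends on the case report form, which is not in the documents. A reader might infer that the SAP deliberately counts toe amputations; the documents do not support that. What stands is that the written event and censoring rule contain no filter, and a programmer has no instruction to apply one.

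A reader might also infer that the SAP departs from the protocol by counting the untreated leg. It does not: the protocol endpoint names no leg either, so restricting to the injected leg would be a new decision rather than a correction of the SAP.

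A broader count also has a place. Both documents state an objective on the incidence and extent of lower leg amputation, which is not limited to major ones. That supports reporting minor amputations as well, but not in place of the stated endpoint.

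Finally, this is one unranked secondary endpoint in a 50-patient study, and site and leg appear to be recorded, so the events might be separated later. But if the definition were chosen after unblinding, the choice would be post hoc.

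**Conclusion.** The concern holds for the level of amputation. The protocol endpoint is major limb amputation. SAP 10.2.7, Table 11.1.1 and Figure 1, followed as written, would analyse amputation of any level and could let a minor amputation hide a later major one. That is a conflict between the documents and should be corrected.

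The missing definition of *major* and the missing statement on the leg are gaps common to both documents. Treating a toe amputation as minor is the usual reading, not one that the documents give.

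The only size that rests on the documents is the effect of a single patient: up to 10 points on placebo and 5 in an active arm. A reader might want a figure for the overall inflation of the rate, but any such figure depends on assumed rates and on how far minor and major amputations fall in the same patients. The illustration above shows the direction under one set of assumptions and is not an estimate.

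**What to change.** In SAP 10.2.7, Tables 11.1.x and Figure 1:

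- Define the event as first major limb amputation, as in the protocol, and censor patients without one.
- Define *major* by anatomical level, and apply that definition in 10.1.2 and the five other imputation sections. A cross-reference to 10.1.2 alone would not help, because the word is undefined there too.
- State before unblinding whether the analysis is of the treated leg or of either leg, and report index and non-index leg separately. Clarify the protocol endpoint to match.
- Tabulate minor amputations separately, which serves the incidence-and-extent objective.

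The cost is wording and table titles. The data appear to be collected: Listing 39 has surgical site and leg for vascular procedures, and Listing 27 has the study leg. The small downside is fewer events in an analysis that is already small.
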